**Table 6 Prohibited concomitant medications**

Prohibited medication/class of drug	Usage
EGFR TKIs	Should not be given concomitantly. Should be used with caution in the 90 days after the last dose of durvalumab. Increased incidences of pneumonitis (with third generation EGFR TKIs) and increased incidence of transaminase increases (with first-generation EGFR TKIs) have been reported when durvalumab has been given concomitantly.
Herbal and natural remedies, which may have immune-modulating effects	Should not be given concomitantly unless agreed by the Sponsor.

AE Adverse event; CRT Chemoradiation therapy; CTLA-4 Cytotoxic T-lymphocyte antigen 4; EGFR Epidermal growth factor receptor; I-O Immunology; IP Investigational product; PD-1 Programmed cell death 1; PD-L1 Programmed cell death ligand 1; SoC Standard of care; TKI Tyrosine kinase inhibitor.

**Table 7 Restricted concomitant medications**

Restricted medication/class of drug	Concern
Strong or moderate CYP3A inhibitors	Known strong CYP3A inhibitors (eg, itraconazole, telithromycin, clarithromycin, boosted protease inhibitors, indinavir, saquinavir, nelfinavir, boceprevir, telaprevir) or moderate CYP3A inhibitors (ciprofloxacin, erythromycin, diltiazem, fluconazole, verapamil) should not be taken with olaparib. If there is no suitable alternative concomitant medication, then the dose of olaparib/placebo should be reduced for the period of concomitant administration. The dose reduction of olaparib/placebo should be recorded in the eCRF with the reason documented as concomitant CYP3A inhibitor use (see Section 6.7.2).
Strong or moderate CYP3A inducers	Strong (eg, phenobarbital, phenytoin, rifampicin, rifabutin, rifapentine, carbamazepine, nevirapine, enzalutamide, and St John's Wort) and moderate CYP3A inducers (eg, bosentan, efavirenz, and modafinil) of CYP3A should not be taken with olaparib. If the use of any strong or moderate CYP3A inducers is considered necessary for the patient's safety and welfare, this could diminish the clinical efficacy of olaparib. If a patient requires use of a strong or moderate CYP3A inducer, then they must be monitored carefully for any change in efficacy of olaparib.

**Table 7 Restricted concomitant medications**

Restricted medication/ class of drug	Concern
P-gp inhibitors	It is possible that co-administration of P-gp inhibitors (eg, amiodarone, azithromycin) may increase exposure to olaparib. Caution should therefore be observed.
Effect of olaparib on other drugs	
Based on limited in vitro data, olaparib may increase the exposure to substrates of CYP3A4, P-gp, OATP1B1, OCT1, OCT2, OAT3, MATE1, and MATE2K.
 
Based on limited in vitro data, olaparib may reduce the exposure to substrates of CYP3A4, CYP2B6, CYP2C9, CYP2C19, and P-gp.
 
The efficacy of hormonal contraceptives may be reduced if coadministered with olaparib.
 
Caution should therefore be observed if substrates of these isoenzymes or transporter proteins are coadministered.
 
Examples of substrates include:
 
 
● CYP3A4 – hormonal contraceptive, simvastatin, cisapride, cyclosporine, ergot alkaloids, fentanyl, pimozone, sirolimus, tacrolimus, quetiapine
 
● CYP2B6 – bupropion, efavirenz
 
● CYP2C9 – warfarin
 
● CYP2C19 - lansoprazole, omeprazole, S-mephenytoin
 
● P-gp - simvastatin, pravastatin, digoxin, dabigatran, colchicine
 
● OATP1B1 - bosentan, glibenclamide, repaglinide, statins, valsartan
 
● OCT1, MATE1, MATE2K – metformin
 
● OCT2 - serum creatinine
 
● OAT3 - furosemide, methotrexate
 

Anticoagulant therapy	Patients who are taking warfarin may participate in this study; however, it is recommended that INR be monitored carefully at least once per week for the first month, then monthly if the INR is stable. Subcutaneous heparin and low-molecular-weight heparin are permitted.
Anti-emetics/ Anti-diarrheals	From screening part 2 onward, should a patient develop nausea, vomiting, and/or diarrhea, then these symptoms should be reported as AEs (see Section 8.3) and appropriate treatment of the event should be given.

**Table 7 Restricted concomitant medications**

Restricted medication/ class of drug	Concern
Palliative radiotherapy	Palliative radiotherapy may be used for the treatment of pain at the site of bony metastases or symptomatic pelvic soft tissue mass(es) that were present at baseline, provided the Investigator does not feel that these are indicative of clinical disease progression during the study period. Study treatment should be discontinued for a minimum of 3 days before a patient undergoes therapeutic palliative radiation treatment. Study treatment should be restarted within 4 weeks as long as any bone marrow toxicity has recovered.
Administration of other anticancer agents	Patients must not receive any other concurrent anticancer therapy, including investigational agents, while on study treatment. Patients may continue the use of bisphosphonates or denosumab for bone disease and corticosteroids for the symptomatic control of brain metastases provided the dose is stable before and during the study and they were started at least 4 weeks prior to beginning study treatment.
Subsequent therapies for cancer	Details of first and subsequent therapies for cancer and/or details of surgery for the treatment of the cancer, after discontinuation of treatment, will be collected. Reasons for starting subsequent anticancer therapies including access to other PARP inhibitors or investigational drugs will be collected and included in the exploratory assessments of OS.

AEs Adverse events; CYP Cytochrome; eCRF electronic case report form; INR International Normalized Ratio; OS Overall survival; P-gp Permeability glycoprotein; PARP Poly (ADP ribose) polymerization.

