**Table 6 Prohibited concomitant medications**

Prohibited medication/class of drug	Usage
Any investigational anticancer therapy other than those under investigation in this study	Should not be given concomitantly while the patient is on study treatment.
mAbs against CTLA-4, PD-1, or PD-L1 other than those under investigation in this study	Should not be given concomitantly while the patient is on study treatment.
Any concurrent chemotherapy, radiotherapy, immunotherapy, or biologic or hormonal therapy for cancer treatment other than those under investigation in this study	Should not be given concomitantly while the patient is on study treatment. (Concurrent use of hormones for non-cancer-related conditions [eg, insulin for diabetes and hormone replacement therapy] is acceptable. Local treatment of isolated lesions, excluding target lesions, for palliative intent is acceptable [eg, by local surgery or radiotherapy].)
Live attenuated vaccines	Should not be given through 30 days after the last dose of the IP.
Immunosuppressive medications, including, but not limited to, systemic corticosteroids at doses exceeding 10 mg/day of prednisone or equivalent, methotrexate, azathioprine, and tumor necrosis factor- $\alpha$ blockers	
Should not be given concomitantly, or used for premedication prior to the I-O infusions. The following are allowed exceptions:
 
 
• Use of immunosuppressive medications for the management of IP-related AEs.
 
• Short-term premedication for patients receiving SoC CRT, in which the prescribing information for the agent requires the use of steroids for documented hypersensitivity reactions, nausea/vomiting, prophylaxis, etc.
 
• Use in patients with contrast allergies.
 
• In addition, use of inhaled, topical, and intranasal corticosteroids are permitted.
 
 
A temporary period of steroids will be allowed if clinically indicated and considered to be essential for the management of non-immunotherapy related events experienced by the patient (eg, chronic obstructive pulmonary disease, radiation, nausea, etc.).

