**Table 8 Supportive medications**

Supportive medication/class of drug	Usage
Concomitant medications or treatments (eg, acetaminophen or diphenhydramine) deemed necessary to provide adequate prophylactic or supportive care, except for those medications identified as “prohibited,” as listed above	To be administered as prescribed by the Investigator
Best supportive care (including antibiotics, nutritional support, correction of metabolic disorders, optimal symptom control, and pain management [including palliative radiotherapy to non-target lesions, etc.]	Should be used, when necessary, for all patients

Inactivated viruses, such as those in the influenza vaccine	Permitted
---	-----------

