### **Objective response rate**

ORR (per RECIST 1.1 using Investigator assessments) is defined as the number (%) of patients with at least 1 visit response of CR or PR. Data obtained up until progression, or the last evaluable assessment in the absence of progression, will be included in the assessment of ORR. Patients who go off treatment without progression, receive a subsequent therapy, and then respond will not be included as responders in the ORR.

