### Special cases:

- For TL measurable in 2 or 3 dimensions, always report the longest diameter. For pathological lymph nodes measurable in 2 or 3 dimensions, always report the short axis.
- If the CT/MRI slice thickness used is >5 mm, the minimum size of measurable disease at baseline should be twice the slice thickness of the baseline scan.
- If a TL has completely disappeared, the longest diameter should be recorded as 0 mm. If a lesion appears in the same location on a subsequent scan, it will be recorded as a new lesion.
- If a TL splits into 2 or more parts, then record the sum of the diameters of those parts.
- If 2 or more TLs merge, then the sum of the diameters of the combined lesion should be recorded for 1 of the lesions and 0 mm recorded for the other lesion(s).
- If a TL is believed to be present and is faintly seen but too small to measure, a default value of 5 mm should be assigned. If an accurate measure can be given, this should be recorded, even if it is below 5 mm.
- If a TL cannot be measured accurately due to it being too large, provide an estimate of the size of the lesion.
- When a TL has had any intervention, eg, definitive radiotherapy, embolization, surgery, during the study, the size of the TL should still be provided where possible and the intervention recorded in the RECIST 1.1 case report form (see Not evaluable in [Table 19](#)). If a TL has been completely removed (surgery), the longest diameter should be recorded as 0 mm.

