**Table 19 Evaluation of target lesions**

Complete response (CR)	Disappearance of all TLs since baseline. Any pathological lymph nodes selected as TLs must have a reduction in short axis to <10 mm.
Partial response (PR)	At least a 30% decrease in the sum of the diameters of TL, taking as reference the baseline sum of diameters
Stable disease (SD)	Neither sufficient shrinkage to qualify for PR nor sufficient increase to qualify for PD
Progression of disease (PD)	At least a 20% increase in the sum of diameters of TLs, taking as reference the smallest sum on study (this includes the baseline sum if that is the smallest on study). In addition to the relative increase of 20%, the sum must also demonstrate an absolute increase of at least 5 mm.
Not evaluable (NE)	Only relevant if any of the TLs at follow-up were not assessed or NE (eg missing anatomy) or had a lesion intervention at this visit. Note: If the sum of diameters meets the progressive disease criteria, progressive disease overrides NE as a TL response.

TL Target lesion

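### Table 7 omits the target-lesion exclusion that Table 6 sets for palliative radiotherapy, and Table 19 makes a treated target lesion not evaluable only at the visit of the intervention

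*Protocol*

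**What the plan says.** Three tables in Protocol Section 6.6 deal with palliative radiotherapy on study treatment.

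- **Table 6 (prohibited)** bars concurrent radiotherapy for cancer, with one exception: "Local treatment of isolated lesions, excluding target lesions, for palliative intent is acceptable [eg, by local surgery or radiotherapy".
- **Table 7 (restricted)** states: "Palliative radiotherapy may be used for the treatment of pain at the site of bony metastases or symptomatic pelvic soft tissue mass(es". The sites must have been present at baseline, and the permission holds "provided the Investigator does not feel that these are indicative of clinical disease progression during the study period". Target lesions are not mentioned.
- **Table 8 (supportive)** lists, under pain management, "including palliative radiotherapy to non-target lesions, etc".

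Appendix F (Target lesions, Special cases) asks that a target lesion with an intervention still be measured where possible and that the intervention be recorded, and it points to the NE row of Table 19. The same item adds: "If a TL has been completely removed (surgery), the longest diameter should be recorded as 0 mm". The NE row applies when a target lesion was not assessed, was not evaluable, "or had a lesion intervention at this visit". A note says that progression by the sum of diameters overrides NE.

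Under Section 9.4.1.1, one visit of CR or PR makes a responder for ORR. The stated exclusion is: "Patients who go off treatment without progression, receive a subsequent therapy, and then respond will not be included as responders in the ORR".

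**The concern.** The protocol both excludes irradiation of a target lesion (Table 6) and appears to allow it (Table 7). Entry requires only one target lesion (Section 5.1, criterion 9), and the pelvis is part of the scheduled imaging. The mass a site irradiates under Table 7 may therefore be the lesion that decides the patient's visit responses. Sites that rely on different tables would treat that lesion differently.

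The response rules then leave a gap. NE is tied to the visit of the intervention, and nothing says what happens to the altered diameter afterwards. Investigator RECIST 1.1 is the source for PFS (primary), ORR, DoR and PFS6, and central review is at the sponsor's discretion (Section 8.1.1). At stake is whether shrinkage caused by radiation can be counted as drug effect.

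**Working it through.** The protocol states no figure on this point, so the check is a reading of the rules followed by an illustration with assumed lesion sizes.

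**1. Is a target lesion open to radiotherapy?**

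| Place | Radiotherapy to a target lesion |
|---|---|
| Table 6 | expressly outside the exception |
| Table 7 | pelvic masses present at baseline allowed; target status not addressed |
| Table 8 | names non-target lesions only; contains no prohibition |

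The Table 7 proviso concerns suspected progression, not target status, so it does not supply the missing exclusion.

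**2. What happens to the visit response?**

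- At the intervention visit the target-lesion response is NE. Table 21 then gives an overall NE unless there is non-target progression or a new lesion, and progression by the sum overrides NE.
- At the next visit there is no intervention at that visit. Read literally, the NE ground has lapsed and the measured diameter is in the sum.
- Table 19 takes PR from the baseline sum (at least a 30% decrease) and PD from the smallest sum on study (at least a 20% increase and at least 5 mm). Neither definition sets a treated lesion aside.
- The ORR exclusion covers patients who have gone off treatment. Table 7 has study treatment paused for radiotherapy and then restarted, so such a patient is not caught.

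The protocol recognises the measurement problem elsewhere. Appendix F treats lesions irradiated before baseline as typically non-measurable, because local post-radiation change can alter their size.

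**3. Size per patient, if NE does not carry forward.** Sizes are assumed, and the other target lesion is stable. Change = (later sum − baseline sum) / baseline sum.

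| Pelvic + other at baseline (mm) | Pelvic lesion halved | Pelvic lesion 0 mm |
|---|---|---|
| 20 + 60 = 80 | 70, −12.5%, SD | 60, −25.0%, SD |
| 30 + 40 = 70 | 55, −21.4%, SD | 40, −42.9%, PR |
| 40 + 30 = 70 | 50, −28.6%, SD | 30, −57.1%, PR |
| 60 + 20 = 80 | 50, −37.5%, PR | 20, −75.0%, PR |

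If the irradiated mass is the only target lesion, halving it is −50%, a PR by itself. If NE does carry forward, every entry is NE.

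**4. Effect on progression.** The direction depends on timing. Take 60 + 20 = 80 mm at baseline, with the 20 mm node growing to 38 mm.

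- Mass untreated: 60 + 38 = 98; 98/80 = +22.5% and +18 mm, which is PD.
- Mass at 15 mm, node already 38 mm at the first sum that counts: 15 + 38 = 53; 53/80 = −33.75%, which is PR.
- Mass at 15 mm, node still 20 mm at that first sum: the nadir is 35 mm. Later 53/35 = +51% and +18 mm, which is PD.

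For 53 mm to escape PD, the earlier smallest sum must exceed 53/1.2 ≈ 44 mm. The node must then already exceed about 44 − 15 = 29 mm at that scan. A lower nadir otherwise brings PD forward. For 40 + 30 mm with the first lesion at 0 mm, the growth needed falls from 0.2 × 70 = 14 mm to 0.2 × 30 = 6 mm.

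**5. Trial scale.** One false responder in an arm of 75 moves that arm's ORR by 1/75 = 1.3 percentage points. The protocol gives no number of such patients.

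**The case against.** The strongest reply is that Tables 6 and 7 can be read together: bone or pelvic sites present at baseline, subject to the general exclusion of target lesions. Table 7 never says that a target lesion may be irradiated. Appendix F adds a safeguard by sending a treated target lesion to NE with progression overriding, and how long NE lasts could be settled in the SAP, which is not shown. Other rules narrow the route further. The Table 7 proviso applies, clinical progression requires both drugs to stop (Section 7.1), and patients treated through progression may not have concurrent radiation without consulting the sponsor (Appendix F). The trial is double-blind, and nothing suggests that such treatment would fall mainly in one arm.

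Much of this stands, and it limits the point. A reader might infer any of the following, none of which the protocol supports:

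- **That Table 8 forbids irradiating target lesions.** It only implies this; the express exclusion is in Table 6.
- **That Appendix F simply accepts a treated lesion as shrinkage.** It does not at the intervention visit. Afterwards the wording is literal but not explicit.
- **That target lesions may be resected on study treatment.** Table 7 covers radiotherapy only, and Table 6 excludes local surgery of target lesions. The 0 mm rule matters only for surgery outside these permissions.
- **That local therapy generally hides progression.** Step 4 shows it can equally bring PD forward.
- **That a shift in ORR or PFS can be estimated.** Any frequency would be invented.

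The reply does not remove the conflict. Sites act on the concomitant-therapy tables, and an SAP cannot reconcile those. Table 19 ties its rule to a single visit in the protocol itself.

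**Conclusion.** The point holds in a limited form. Table 7 lacks the target-lesion exclusion that Table 6 states and Table 8 implies, so the protocol both excludes and appears to allow irradiation of a target lesion. Table 19 protects only the visit of the intervention. Read literally, the altered diameter then returns to the sum and the nadir, where it can yield a PR that counts for ORR or shift the PD reference in either direction. For an affected patient the change can cross a response threshold, as the assumed sizes show. At trial level the size cannot be derived from the protocol and is probably modest. The conclusion rests on two assumptions: that some irradiated pelvic masses are target lesions, and that assessors apply the Table 19 wording as written.

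**What to change.** 1. Reconcile Tables 6, 7 and 8 so that one statement governs local treatment of target lesions. Which clinical rule applies is for the sponsor.
2. In Table 19, extend the NE ground to an intervention at this or any earlier on-study visit, so that shrinkage of a treated target lesion cannot support CR or PR or lower the nadir. One way to do this is to carry that lesion in the sum at no less than its last size before treatment. In the 60 + 20 mm example this gives 60 + 38 = 98 against 80, +22.5%, which is PD whatever the timing.
3. Keep PD overriding NE, including PD from the remaining target lesions, non-target lesions and new lesions.
4. State that visits scanned but rated NE for this reason are not missed visits under the PFS rule in Section 9.4.1.1. That rule censors events after two or more consecutive missed visits, and Section 9.4.2.1 describes these as non-evaluable assessments. Without this statement, a lasting NE could censor true later progressions or deaths, especially in patients with a single target lesion.

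The cost is protocol wording and a change to the response derivation. Interventions are already recorded on the RECIST form. A few patients lose later response evaluability, and those with no event could be censored at their last evaluable scan before the intervention.

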**Table 8 Supportive medications**

Supportive medication/class of drug	Usage
Concomitant medications or treatments (eg, acetaminophen or diphenhydramine) deemed necessary to provide adequate prophylactic or supportive care, except for those medications identified as “prohibited,” as listed above	To be administered as prescribed by the Investigator
Best supportive care (including antibiotics, nutritional support, correction of metabolic disorders, optimal symptom control, and pain management [including palliative radiotherapy to non-target lesions, etc.]	Should be used, when necessary, for all patients

Inactivated viruses, such as those in the influenza vaccine	Permitted
---	-----------

### 6.6.1 Other concomitant treatment

Medication other than that described above, which is considered necessary for the patient's safety and well-being, may be given at the discretion of the Investigator and recorded in the appropriate sections of the eCRF.

In addition, any unplanned diagnostic, therapeutic, or surgical procedure performed during the study period must be recorded in the eCRF.

### 6.6.2 Durvalumab drug-drug interactions

There is no information to date on drug-drug interactions with durvalumab either nonclinically or in patients. As durvalumab is a mAb and therefore a protein, it will be degraded to small peptides and amino acids and will be eliminated by renal and reticuloendothelial clearance. It is therefore not expected that durvalumab will induce or inhibit the major drug metabolizing cytochrome P450 pathways. As a result, there are no expected PK drug-drug interactions. The MOA of durvalumab involves binding to PD-L1, and therefore, significant pharmacodynamic drug interactions with the commonly administered concomitant medications are not expected. Despite this, appropriate clinical monitoring in all of the planned clinical studies will be conducted to evaluate any potential drug-drug interactions.

## 6.7 Dose modification

### 6.7.1 Durvalumab

Dose delays are permitted for immune-oncology (IO) therapy (see Dosing Modification and Toxicity Management Guidelines). However, **dose reduction is not permitted.**

### 6.7.2 Olaparib

When dose reduction is necessary, patients with  $\text{CrCl} \geq 51$  mL/min dosed with 300 mg BID will take one 150-mg tablet and one 100-mg tablet (250 mg BID) or two 100-mg tablets (200 mg BID). Patients with  $\text{CrCl} \geq 31$  mL/min but  $< 51$  mL/min dosed with 200 mg BID will take one 150-mg tablet (150 mg BID) or one 100-mg tablet (100 mg BID) (see Sections [6.7.2.1](#) and [8.4.5.2](#)). Patients

initiating olaparib at 200 mg BID due to reduced CrCl may escalate the dose to 300 mg BID at the beginning of the next treatment cycle if the CrCl increases to  $\geq 51$  mL/min. Intracycle dose escalation of olaparib is not permitted.

